4.4 Rationale for Study

CT1812 was shown to be safe and well tolerated in a study of healthy volunteers and in Phase 1 studies of participants with mild to moderate Alzheimer's disease. This Phase 2 study is designed to evaluate the safety of two doses of CT1812 administered once daily for 6 months in adults aged 50 to 85 who have been diagnosed with mild to moderate Alzheimer's disease (the targeted clinical indication for CT1812). Randomized participants will receive 100 mg of CT1812, 300 mg of CT1812, or placebo once daily for 182 days. Exploratory endpoints that evaluate the effect of CT1812 on biomarkers are also included.

4.5 Rationale for Selected Doses

Based on brain receptor occupancy studies in animals, the daily dose of 300 mg/day is projected to exceed 95% occupancy while the 100 mg/day dose is projected to exceed 80% receptor occupancy. In the Phase 1 multiple dose 2-week trial, doses exceeding 300 mg/day were well-tolerated in both younger (≤ 64 years of age) and older (≥ 65 years of age) s. In the phase 1 AD

trial, tolerability was also acceptable with no serious adverse events observed at doses exceeding 300 mg/day.

5 STUDY OBJECTIVES

5.1 Primary Objectives

• To assess the safety and tolerability of CT1812 in participants with mild to moderate Alzheimer's disease.

5.2 Secondary Objectives

 To assess target engagement and identify pharmacodynamic effects of CT1812 on CSF biomarkers.

5.3 Exploratory Objectives

- To assess the efficacy of CT1812 as a treatment for mild to moderate Alzheimer's disease.
- To characterize the PK profile of CT1812 in plasma.

6 STUDY TYPE AND DESIGN

6.1 Study Type

This is a multi-center Phase 2, randomized, double-blind, placebo-controlled, parallel-group study.

6.2 Endpoints

6.2.1 Safety Endpoints

- The incidence and severity of adverse events.
- The change in usage of concomitant medications.
- Changes in vital signs.
- Changes in physical exam findings.
- Changes in electrocardiogram findings.
- Changes in clinical laboratory testing (serum chemistry, hematology, urinalysis).

Changes in the Columbia Suicide Severity Rating Scale (C-SSRS).

6.2.2 Efficacy Endpoints

- Mini Mental State Exam (MMSE).
- ADAS-cog 11 and ADAS-cog 13 (Delayed Recall and digit cancellation added to ADAS-11 in the ADAS-13).
- Neuropsychological Test Battery (NTB). NTB includes Trails A & B, Digit Span, Letter & Category Fluency (COWAT and CFT).
- ADCS-Clinical Global Impression of Change (CGIC).
- ADCS-Activities of Daily Living (ADCS-ADL).

6.2.3 Pharmacokinetic/Pharmacodynamic Endpoints

Pharmacokinetics:

- CT1812 CSF/plasma concentration ratio (end of study only).
- Changes in pre-dose/trough level CT1812 plasma concentrations.

• Pharmacodynamics:

 CSF- Aβ, tau, phospho-tau, neurogranin, synaptotagmin, SNAP25 (synaptosomalassociated protein 25), Neuro Filament Light Chain (NFL), Aβ oligomers. Other exploratory target engagement biomarkers may also be evaluated.

6.3 Study Design

This is a double-blind, placebo-controlled parallel-group trial in adults with mild to moderate AD. Participants will be screened for eligibility by physical, laboratory and psychometric and neurologic examinations, neuroimaging, and pre-drug CSF and blood samples obtained ≤42 days prior to randomization at Baseline/Day 1. After having met all inclusion criteria, and none of the exclusion criteria, participants will be randomized to one of three treatment arms (CT1812 at doses of 100 or 300 mg/d or placebo, n=48/group). The first dose of study drug will be administered in the clinic after all baseline procedures have been conducted. With the exception of clinic visits days, for the remainder of study days, participants will ingest study drug each morning at home with or without food. Participants and their caregivers/study partner will

return to the clinic for repeat psychometric/neurologic testing, safety procedures and PK and PD sample collection at the intervals described below.

Up to 144 participants will be enrolled.

Participants in Part A and B will return to the clinic twice in the first week after baseline, weekly for three weeks, bimonthly until Day 70, then every four weeks until Day 182 (See Table 1). A follow up visit will occur approximately 30 days after the end of treatment.

Participants in Part C will return to the clinic for Visit 3 on Day 7 and Day 14 after baseline, followed by twice-monthly visits until Day 70, then every four weeks until Day 182 (See Table 1). A follow up visit will occur approximately 30 days after the end of treatment.

Participants who prematurely discontinue the study for any reason will be asked to attend a final safety and efficacy visit.

6.3.1 Re-Screening Activities

Participants who initially do not meet all enrollment criteria for this study may be permitted to rescreen. Re-screening may be permitted on a case-by-case basis following a discussion between the PI and the Medical Monitor regarding whether a participant remains potentially eligible to participate in the study. A participant who is re-screened is not required to sign another ICF if the re-screening occurs within 30 days from the previous ICF signature date. There is no minimum period of time a participant must wait to re-screen for the study. The participant must meet all eligibility criteria at the time of re-screening in order to qualify for the study. Depending upon the time from the last screening visit, the Medical Monitor will determine what assessments need to be repeated.

7 STUDY DRUG

7.1 Supply and Storage

Study drug will be provided in bottles containing capsules of CT1812 active equivalent to 50 mg or 150 mg of the CT1812 free base and its matching placebo. Study drug will be provided in bottles with desiccant packs. The treatment label on the bottle will include a study reference code (protocol number), drug identifier, quantity of capsules, and lot number at minimum, as well as pertinent information according to local regulations. The expiry or use-by date will be stored in the IRT (IVRS/IWRS) or according to local regulations. Study drug should not be used after the

expiry or use-by date. All packaged and labelled supplies will be formally released in accordance with both Good Manufacturing Practice (GMP) and Good Clinical Practice (GCP) guidelines.

The study drug should be stored in its original packaging at refrigerated temperatures (2 °C- 8 °C [32 °F -40 °F]), with daily minimum and maximum temperature logs maintained at the site. The investigator, or an approved representative (e.g., pharmacist), will ensure that all study drugs are stored and dispensed in accordance with local regulations concerning the storage and administration of investigational drugs. All drug supplies must be kept in a secure locked area under recommended storage conditions with access limited to those authorized by the investigator.

7.2 Administration

CT1812 or matching placebo will be administered orally as a single daily dose for 6 months. All participants will ingest the first dose in the clinic and be observed for 2 hours. A single daily dose consists of 2 capsules of study drug. Two (2) capsules will be swallowed with ~240 mL of water with or without food. Daily outpatient dosing should occur in the morning (i.e., prior to 12 pm). To ensure appropriate specimen collection times relative to dosing on clinic days, participants will be asked to bring their study medication to clinic visits and to take their medication at the clinic upon the instruction of the site staff. On "Drug Dispensation" clinic visits drug accountability will be completed for the bottle returned by the participant and the "in office dose administration" will be taken for that visit from the newly assigned bottle.

7.2.1 Safety Stopping Rules

Dosing may be terminated by the Sponsor at the recommendation of the DSMB (Data Safety and Monitoring Board) based on safety and tolerability data, or at the discretion of the Sponsor; as a result, there are no study-specific stopping rules defined in this protocol.

The occurrence of any one of the following events will result in a review of study safety information to date by the Sponsor and DSMB.

- Two occurrences of the same or similar serious adverse event (SAE) assessed as
 probably or possibly related to dosing with investigational product.
- Two or more different participants with the same or similar severe AE assessed as
 probably or possibly related to dosing with the investigational product.

 Four or more participants with the same or similar moderate AE which is possibly or probably related to dosing with investigational product.

Under these circumstances, the Sponsor and DSMB will review the available safety data and recommend whether dosing should continue, or if study drug administration should be terminated, or if additional monitoring procedures or safety precautions need to be employed. Selective unblinding of the participants in the study may be performed by the Sponsor and DSMB to determine if the SAEs/AEs are isolated to a single dose group or if they occurred in placebo participants.

The study or a dose group may also be terminated if the Sponsor and DSMB determine that any adverse event(s) are occurring that are intolerable or pose a medically unacceptable safety risk.

For individual participants:

Any participant who develops the following liver function test (LFT) laboratory abnormalities will not receive any additional doses and will be monitored until resolution of the AE or the return of laboratory abnormality to the acceptable screening value(s).

- Elevated ALT or AST greater than 5 X Upper Limits of Normal (ULN)
- elevated ALT or AST greater than 3 X ULN in combination with total bilirubin > 2 X ULN or INR > 1.5 X ULN
- ALT or AST > 3 X ULN with the appearance of fatigue, nausea, vomiting, right upper quadrant pain or tenderness, fever, rash, and/or eosinophilia (>5%)

Serial monitoring of ALT/AST/bilirubin and INR will be performed, initially with repeat values within 4 days of discontinuation of study drug. If LFTs are still elevated 4 days post-study drug interruption, participants should have LFTs checked again 4 days later (+/- 1 day). The site investigator and Medical Monitor should agree to a plan for further LFT monitoring depending on whether the LFTs are still increasing or trending towards normal. Repeat testing should be carried out until LFTs have normalized. The LFTs in this instance can also be run locally for more rapid turnaround.

In the event a reversible etiology is found to explain the elevated liver enzymes (such as a common bile duct stone), drug may be restarted following normalization of LFTs, and after discussion between the Medical Monitor and site PI.

Study drug will be temporarily discontinued if a participant does not achieve the aforementioned levels of elevated transaminases but has an elevation of ALT or AST >3 X

ULN. These participants will have their liver function retested within 4 days after their last dose of study drug. If transaminases are still elevated 4 days post-study drug interruption, participants will have LFTs checked again 4 days later (+/- 1 day), and the site PI and Medical Monitor will agree to a plan for further monitoring of the findings. The LFTs in this instance can also be run locally for more rapid turnaround.

LFTs do not need to be intensively monitored when ALT and AST are ≤ 3 X ULN with no elevation of bilirubin, however the investigator and the Medical Monitor will formulate a plan for serial testing of LFTs. Cessation of dosing is not required in this circumstance but may be temporarily interrupted at the discretion of the investigator.

7.3 Drug Accountability

Participants will return all study bottles and unused study drug at each clinic visit for drug accountability to be performed. The Investigator or their appointed designee is responsible for ensuring that deliveries of study drug are correctly dispensed and recorded, that the product is handled and stored safely and properly, and that it is only being given to participants in accordance with this protocol.

Sites will keep a current log of drug accountability recording:

- What drug supply was received from the Sponsor.
- What drug supply was dispensed to each participant.
- What drug supply is current in inventory.
- What drug supply was destroyed or returned to the Sponsor for destruction.

Note: Drug accountability is the responsibility of the Investigator; a written account will be required for all discrepancies.

The Sponsor's designated Monitor must verify all accountability records during periodic monitoring visits. Unused and used study drug must be stored on site until such accountability has taken place and authorization is received from the Sponsor or Sponsor's designee that the study drug may be returned or destroyed.

7.4 Overdose/Toxicity Management

No specific pharmacologic antagonist or antidote exists for CT1812 or sigma-2 modulators in general. Therefore, overdose or clinical toxicity should be managed with supportive care and

pharmacologic treatments directed at specific symptoms (i.e. benzodiazepines for agitation or antipyretics for fever).

7.5 Blinding, Randomization and Matching Participants

This is a double-blind, placebo-controlled study. Study drug will consist of CT1812 and a matching placebo. The placebo will be identical in appearance to the active CT1812.

The non-blinded statistician assigned to the trial will generate a list with the appropriate number of 4-digit individual study IDs randomly for each arm, randomly assigned to either active or placebo treatment.

Should any participant withdraw from the study prior to study completion, the participant may be replaced, at the sponsor's discretion. The replacement participant will be given the same treatment assignment (by the unblinded statistician) as the withdrawn participant.

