9 STUDY POPULATION

9.1 Number of Participants

Up to 144 participants will be randomized. Additional participants may be added to replace participants with significant disruption to their visit schedule due to COVID or if there are unanticipated dropouts.

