9.6 Procedures for Replacing Participants Who Withdraw Prematurely

Participants who withdraw from the study prior to dosing may be replaced after consultation with the Sponsor. If a participant is replaced, instructions in Section 7.5 will be followed for randomization and assignment of a study number.

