#### 3.5. Method of Assigning Participants to Treatment Groups

Participants will be randomized in a 1:1:1 ratio to CT1812 100 mg/day, CT1812 300 mg/day or placebo. The placebo will be identical in appearance to the active CT1812. The unblinded statistician assigned to the trial will generate a randomization list with the appropriate number of 4--digit individual study identification numbers (IDs) for each arm, randomly assigned to one of the treatment arms.

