#### 3.6. Blinding and Unblinding

This is a double-blind study. All participants, investigators, and study personnel involved in the conduct of the study will be blinded to treatment assignment, with the exception of a specified unblinded statistician who will generate and have access to the randomization code. The unblinded study personnel will not otherwise participate in study procedures or data analysis prior to unblinding of the study data.

If a safety stopping rule (defined in Section 7.3.1 of the study protocol) is achieved, selective unblinding of the participants involved may be performed by the Sponsor to determine if the AEs (serious or otherwise) are isolated to a single dose group or if they occurred in placebo participants.

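### A replacement participant inherits the withdrawn participant's arm instead of being randomised, and the protocol gives three different scopes for who may be replaced

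*Protocol*

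**What the plan says.** Allocation of replacements is set in Protocol 7.5: "The replacement participant will be given the same treatment assignment (by the unblinded statistician) as the withdrawn participant". Protocol 9.6 sends replacements to the same rule: "If a participant is replaced, instructions in Section 7.5 will be followed for randomization and assignment of a study number". The SAP describes only ordinary list randomisation and states no exception: "Participants will be randomized in a 1:1:1 ratio to CT1812 100 mg/day, CT1812 300 mg/day or placebo" (SAP 3.5).

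Eligibility for replacement is described in three ways:

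- Protocol 7.5: "Should any participant withdraw from the study prior to study completion, the participant may be replaced, at the sponsor's discretion".
- Protocol 9.6: "Participants who withdraw from the study prior to dosing may be replaced after consultation with the Sponsor".
- Protocol 9.1, repeated in the synopsis, in Protocol 15.2 and in SAP 3.2: "Additional participants may be added to replace participants with significant disruption to their visit schedule due to COVID or if there are unanticipated dropouts".

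On blinding, SAP 3.6 exempts one unblinded statistician and adds: "The unblinded study personnel will not otherwise participate in study procedures or data analysis prior to unblinding of the study data". Selective unblinding after a safety trigger is open to the DSMB (Protocol synopsis), to the sponsor and DSMB (Protocol 7.2.1), or to the sponsor (SAP 3.6). The synopsis also lets the principal investigator unblind in an emergency and then inform the sponsor.

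**The concern.** Fresh randomisation makes the arm of a new participant independent of everything that has happened in the trial. Under Protocol 7.5 the arm depends on an earlier participant's withdrawal. If that withdrawal followed dosing it may have been caused by treatment, so allocation of later enrolees can depend on a treatment effect.

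Two things follow. First, if dropout differs between arms, later enrolees are spread unequally over the arms. Calendar time matters in this trial: Parts A and B have a different visit schedule from Part C, and SAP 6.1.10 defines a pre/post-COVID subgroup. The MMRM in SAP 8.1 contains treatment, visit, baseline score, APOE ε4 status and treatment by visit, with nothing for Part or period. Second, if the withdrawn participant had been unblinded, the replacement's arm could be known before that person is enrolled, and the sponsor, who may be among those unblinded, has discretion over whether to replace.

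The differing scopes add a practical problem. Staff cannot tell which section governs a participant who drops out after dosing.

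**Working it through.** **1. The plan's own figures.** Inputs from Protocol 15.2: 48 per group, difference 3.0, SD 5.4, two-sided alpha 0.05, dropout 15%, pooled CT1812 versus placebo (2:1).

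- Power ≈ Φ(3.0 / [5.4 × √(1/n₀ + 1/n₁)] − 1.96).
- With 48 × 0.85 = 40.8 placebo and 81.6 active: 82.6%. With 40 and 80: 81.8%, or 81.2% by the noncentral t. The stated 81% reproduces, and it already allows for 15% dropout.
- At least one adverse event: 1 − 0.95⁴⁸ = 91.5%, against 91% stated.

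The sample size is therefore not in question.

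**2. How many assignments could be affected.** Assume each dropout is replaced once. With dropout rate d, replacements are 144d and their share of all assignments is 144d / (144 + 144d).

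| Dropout | Replacements | Share of assignments |
|---|---|---|
| 5% (assumed) | 7.2 | 4.8% |
| 15% (protocol) | 21.6 | 13.0% |
| 25% (assumed) | 36.0 | 20.0% |

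**3. What unequal dropout does.** Assume 10%, 15% and 25% dropout in placebo, 100 mg and 300 mg. These rates are illustrative and not in the documents.

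- Dropouts are 4.8, 7.2 and 12.0, in total 24.
- Under the same-arm rule the next replacement goes to those arms with probability 4.8/24 = 0.20, 7.2/24 = 0.30 and 12/24 = 0.50. Fresh randomisation gives one third each.
- Total assigned becomes 52.8, 55.2 and 60.0, against 48 + 24/3 = 56.0 each.
- If all replacements complete, they make up 4.8/48 = 10% of placebo completers and (7.2 + 12.0)/96 = 20% of pooled active completers. If later enrolees differ from earlier ones by δ points in mean change, the crude pooled comparison shifts by about (0.20 − 0.10)δ = 0.10δ. The documents give no value for δ.
- With equal 15% dropout the shares are 7.2/48 = 15% in every arm, and this term vanishes.

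**4. What randomising replacements would cost.** Assume 15% dropout, 22 replacements and no further loss.

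- Same-arm rule: 48 versus 96 completers, power 87.7% (t).
- Fresh 1:1:1 draws (simulation, 41 placebo and 81 active completers plus 22 new): mean power 87.8%, 5th to 95th percentile 86.6% to 88.9%.

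**5. Scopes side by side.**

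| Section | Who may be replaced | Arm defined? |
|---|---|---|
| 7.5 | Any withdrawal before completion | Yes, same arm |
| 9.6 | Withdrawal before dosing | Yes, by reference to 7.5 |
| 9.1 | COVID disruption, or unanticipated dropouts | Unclear for disrupted participants who did not withdraw, because 7.5 speaks of a withdrawn participant |

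**The case against.** **Withdrawal before dosing.** Here reusing the slot is harmless in respect of arm: the slot came from the random list, and an undosed, blinded participant cannot leave because of treatment. This stands, and the point is limited to withdrawals after dosing.

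**Concealment.** A reader might infer that concealment fails for every replacement. The documents do not support that. The unblinded statistician makes the assignment, SAP 3.6 keeps everyone else blinded, and nothing says that a site is told whom a newcomer replaces or that the replacement comes from the same one of about 25 sites. The risk needs a withdrawn participant whose arm is known or can be inferred, and a route for that knowledge.

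**Contradiction.** A reader might take 9.6 as restricting replacement to withdrawals before dosing. It does not use a restricting word. All three rules are permissive and could overlap, so this is wording to reconcile and not three incompatible rules.

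**Consequence.** The primary objective is safety and all efficacy analyses are exploratory. That limits the consequence. It could be added that same-arm replacement protects the 48 active-dosed participants per dose. That carries little weight for withdrawals after dosing, because SAP section 5 keeps anyone with one or more doses in the Safety Population whether or not they are replaced.

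**Conclusion.** The point holds for replacements of participants who withdraw after dosing. Their arm is not randomised, and it can depend on treatment-related dropout in a way that the planned model does not address. The time imbalance arises only if dropout differs between arms, and it biases the comparison only if outcomes drift over the enrolment period. Neither can be computed from the documents.

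The figure of about 22 of about 166 assignments (13%) is an illustration and should not be read as a bound. It would be lower if the sponsor replaces few dropouts: the 15% is already in the sample size, and Protocol 9.1 speaks of unanticipated dropouts. It could be higher if replacements for COVID disruption are added. Nor is it a defect in itself that replacements enrol later, since that is true under any scheme. The defect is that their arm is not drawn at random.

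This should be corrected, but it does not undermine the sample size or the safety objective.

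**What to change.** - In Protocol 7.5, give each added participant the next unused entry on the 1:1:1 randomisation list, whoever is being replaced.
- Write one replacement rule covering withdrawal before dosing, withdrawal after dosing and COVID disruption without withdrawal. Cite it in Protocol 7.5, 9.1 and 9.6 and in SAP 3.5. Align SAP 3.6 with whatever role the unblinded statistician keeps.
- State in SAP section 5 that a replaced participant stays in the Safety Population if dosed, and in the mITT if the existing definition is met (any study drug, a baseline and at least one post-baseline ADAS-Cog 11). The mITT definition itself need not change.
- If replacements have already been assigned under 7.5, report their number by arm and study Part with the disposition data.

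The cost is amendment wording and a longer list. Arms would no longer be exactly equal. In the unequal-dropout illustration, each arm gains 24/3 = 8 replacements, so completers would be 43.2 + 8 = 51.2 (placebo), 40.8 + 8 = 48.8 (100 mg) and 36 + 8 = 44.0 (300 mg) instead of 48 each. Under the 15% illustration, power is essentially the same (87.8% on average against 87.7%).
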